8.5.2 Safety Analysis Populations

The All Subjects as Treated (ASaT) population will be used for the analysis of safety data in this study. The ASaT population consists of all allocated subjects who received at least one dose of study treatment. Subjects will be included in the treatment group corresponding to the study treatment (i.e., treatment duration, if applicable) they actually received for the analysis of safety data using the ASaT population.

At least one laboratory or vital sign measurement obtained subsequent to at least one dose of study treatment is required for inclusion in the analysis of each specific parameter. To assess change from baseline, a baseline measurement is also required.

Details on the approach to handling missing data for safety analyses are provided in Section 8.6 Statistical Methods.

8.6 Statistical Methods

The approach to handling missing data for efficacy analyses is described in Section 8.6.1. A summary of the analysis strategy for efficacy variables is shown in Table 15.

Nominal p-values may be computed for some efficacy analyses as a measure of strength but no formal tests of hypotheses are planned in this study.

The analysis strategy for safety is described in Section 8.6.2.

8.6.1 Statistical Methods for Efficacy Analyses

Missing Values

A missing data point for a given study visit may be due to any one of the following reasons: a visit occurred but data were not collected or were unusable; a visit did not occur; or a subject discontinued from the study before reaching the visit. Subjects who prematurely discontinued the assigned treatment are encouraged to remain in the study for follow-up, if possible.

The HCV RNA outcome is categorized as TND, TD (u), and TD (q). There are 3 types of missing data handled by different approaches.

1. Intermittent missing: If a missing data point is immediately preceded and followed by non-missing HCV RNA outcomes, the missing value would be imputed to the worst outcome of the two. For example, if a missing data point is preceded by TD(q) and followed by TD(u) or TND, then the missing value would be imputed as TD(q); if a missing data point is preceded by TD(u) and followed by TND, then the missing value would be imputed as TD(u); when a missing value is flanked by two TND, then the missing value would be imputed as TND.

2. Non-intermittent missing related to the study drug: For missing values due to premature study discontinuations due to treatment related reasons either for safety or efficacy, the missing values will be considered as treatment failures.
3. Non-intermittent missing for reasons unrelated to the study drug: For missing data due to premature study discontinuations with reasons unrelated to treatment such as loss to follow-up, protocol deviation, withdrawal of consent, administrative reasons, etc., the missingness mechanism is unlikely to be related to subjects' response to the HCV treatment, and therefore the missing at random (MAR) assumption is reasonable.

The following two approaches will be used to handle non-intermittent missing data due to premature discontinuations, depending on the analytical strategy, as described in the section below and in [Table 15](#).

1. Treatment-Related Discontinuation = Failure (TRD=F) approach: Subjects with treatment-related missing data (type #2 above) will be considered as failure; whereas the subjects who have the non-treatment-related missing value (type #3 above) and who do not have virologic failure during the observed study period will be excluded from the analysis for the time points following their study withdrawal. Note that subjects with documented virologic failure during the treatment or follow-up period, even if they withdrew prematurely due to reasons not related to study drug, are classified as failures.
2. Missing=Failure (M=F) approach: Subjects with any non-intermittent missing data (i.e., type #2 and #3 above) will be imputed as failures, regardless of the reason for study discontinuation.

In addition, a missing baseline/Day 1 HCV RNA result will be replaced with a screening result, if available.

Proportions of Subjects With Virologic Responses and Virologic Failures

For the primary efficacy analysis, the proportions of subjects achieving SVR₁₂ after 12 weeks of treatment in each treatment arm will be provided and 95% confidence intervals for these rates will be calculated using the Clopper-Pearson method [49]. The same method will be used to analyze all binary endpoints including SVR₂₄ after 12 weeks of treatment.

For all analyses conducted using the PP and mFAS populations, the missing data approach of TRD=F will be utilized. In addition, for all analyses in these two populations, a subject will be considered to have achieved a particular endpoint if the HCV RNA levels for the infection he/she had at baseline are < LLOQ. In other words, if a subject has HCV RNA levels \geq LLOQ at a particular time point, but those RNA levels correspond to an infection that is of a different genotype and/or subtype compared to the infection detected at baseline and the baseline infection has been cleared, then the subject is considered to have achieved response for the given endpoint.

Sensitivity analyses that use the FAS population will utilize the M=F missing data approach. Also, in the FAS analyses, only subjects with HCV RNA levels < LLOQ for any type of HCV infection at a given time point will be considered to have achieved the endpoint.

To estimate the secondary efficacy endpoint of proportion of subjects experiencing virologic failure at FW12 for each treatment arm, 95% CIs for these rates will be calculated based on the mFAS analysis population using the Clopper-Pearson method [49]. The missing data approach of TRD=F described previously will be utilized for this analysis.

Table 15 includes a summary of the key efficacy analyses, and Table 16 includes a summary of the analysis populations and various criteria to assess the primary endpoint (SVR₁₂ after 12 weeks of treatment) and secondary endpoints (SVR₂₄ and proportion of subjects experiencing virologic failure at FW12 after 12 weeks of treatment, respectively).

Table 15 Analysis Strategy for Efficacy Variables

Endpoint/Variable (Description, Time Point)	Primary vs. Supportive Approach [†]	Statistical Method	Analysis Population	Missing Data Approach
Primary				
Proportion of subjects achieving SVR ₁₂ in each treatment arm after 12 weeks of treatment	P	95% Confidence Interval (Clopper-Pearson)	PP	TRD=F [‡]
Proportion of subjects achieving SVR ₁₂ in each treatment arm after 12 weeks of treatment	S	95% Confidence Interval (Clopper-Pearson)	mFAS	TRD= F [‡]
Proportion of subjects achieving SVR ₁₂ in each treatment arm after 12 weeks of treatment	S	95% Confidence Interval (Clopper-Pearson)	FAS	M=F [*]
Secondary				
Proportion of subjects achieving SVR ₂₄ in each treatment arm after 12 weeks of treatment	P	95% Confidence Interval (Clopper-Pearson)	PP	TRD=F [‡]
Proportion of subjects achieving SVR ₂₄ in each treatment arm after 12 weeks of treatment	S	95% Confidence Interval (Clopper-Pearson)	mFAS	TRD= F [‡]
Proportion of subjects achieving SVR ₂₄ in each treatment arm after 12 weeks of treatment	S	95% Confidence Interval (Clopper-Pearson)	FAS	M=F [*]
Proportion of subjects experiencing virologic failure at FW12 in each treatment arm after 12 weeks of treatment	P	95% Confidence Interval (Clopper-Pearson)	mFAS	TRD= F [‡]
mFAS = modified Full Analysis Set FAS = Full Analysis Set PP = Per Protocol [†] P=Primary approach; S=Secondary approach. [‡] TRD=F = Treatment-Related Discontinuation=Failure. [*] M=F = Missing=Failure.				

Table 16 Analysis Populations, Criteria for Response, Non-Response, and Exclusion from Analysis Populations

Analysis Population	Criteria for Response	Criteria for Non-Response	Criteria for exclusion from analysis population
PP (Primary for SVR ₁₂ and SVR ₂₄)	HCV RNA < LLOQ for baseline infection HCV RNA ≥ LLOQ demonstrated to be due to reinfection (after clearance of baseline infection)	HCV RNA ≥ LLOQ for baseline infection*	Subject with important deviations from the protocol including subject discontinued from the study for non-treatment related reasons and other violations such as violation of I/E criteria, use of prohibited concomitant medications (see Section 8.5.1)
mFAS (Supportive for SVR ₁₂ , SVR ₂₄ ; Primary for proportion of subjects experiencing virologic failure at FW12)	HCV RNA < LLOQ for baseline infection HCV RNA ≥ LLOQ demonstrated to be due to reinfection (after clearance of baseline infection)	HCV RNA ≥ LLOQ for baseline infection*	Subject discontinued from the study for non-treatment related reasons.
FAS (Supportive for SVR ₁₂ and SVR ₂₄)	HCV RNA < LLOQ	HCV RNA ≥ LLOQ	Subject did not receive at least one dose of study medication
mFAS = modified Full Analysis Set FAS = Full Analysis Set PP = Per Protocol LLOQ = Lower limit of quantification *Baseline infection: Genotype(s) and subtype(s) present at baseline based on population sequencing and genotyping assay			

Subject Virologic Failure: Non-response, Rebound, Virologic Breakthrough, Relapse and Reinfection

Summary statistics will be provided to describe the rates of occurrence of subject non-response, rebound, virologic breakthrough, and relapse. Definitions for subject non-response, rebound, virologic breakthrough, and relapse are in Section 4.2.3.1.1.2. Reinfection will be defined as having detectable virus of a different genotype than that detected at baseline as determined by sequencing. Those with reinfection will be considered treatment success in the mFAS and PP analyses as long as the baseline infection was achieved HCV RNA < LLOQ.

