The subject's ALT or AST increases to >3x nadir, is >3x ULN (confirmed with repeat test within one week), and is temporally associated with signs or symptoms of liver inflammation that are of moderate or severe intensity and deemed by the investigator to be at least possibly related to study therapy.	Discontinue from Treatment (should continue to monitor in the trial)
The subject's serum creatinine increases to Grade 3 or higher (>1.8x upper limit of normal), confirmed with repeat test within one week.	Discontinue from Treatment (should continue to monitor in the trial)
The subject's creatinine clearance (eGFR) decreases to <30 mL/min/1.73 m ² , confirmed with repeat test within 1 week. Creatinine clearance will be evaluated as an estimated GFR (eGFR), based on the modification of diet in renal disease (MDRD) equation: $eGFR \text{ (mL/min/1.73 m}^2\text{)} = 175 \times (\text{Scr, std})^{-1.154} \times (\text{Age})^{-0.203} \times (0.742 \text{ if female}) \times (1.212 \text{ if black})$ Scr, std: serum creatinine measured with a standardized assay	Discontinue from Treatment (should continue to monitor in the trial)
The subject has a Grade 4 laboratory AE, or a life-threatening clinical AE, or an AE that results in or prolongs an existing in-subject hospitalization, that is assessed to be a study drug-related laboratory or clinical AE.	Discontinue from Treatment (should continue to monitor in the trial)
SAE assessed by the physician investigator as possibly or probably related to study medication. Investigator may continue the subject in the trial, if it is deemed to be in the best interest of the subject to stay on the study treatment after consultation with Sponsor.	May Discontinue from Treatment (should continue to monitor in the trial)
Failure to comply with the dosing, evaluations, or other requirements of the trial.	May Discontinue from Treatment (should continue to monitor in the trial)

NOTE: Clinical management of HIV-1 virologic failure will be handled by site investigators according to current HIV treatment guidelines and local standard of care. Subjects with HIV virologic failure may continue in the study unless there is a requirement for prohibited concomitant medications (see Section 5.5) to construct a new HIV treatment regimen.

Discontinuation from treatment is “permanent.” Once a subject is discontinued, he/she shall not be allowed to restart treatment.

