7.1.5.4 Discontinued Subjects Continuing to be Monitored in the Trial

Discontinuation during Treatment Period

Subjects who discontinue therapy in the trial prior to the last scheduled treatment visit should have an Early Discontinuation visit and then continue into follow-up visits.

At a minimum, the following information should be collected:

- The reason the subject discontinued
- The date of the last dose of study medications from the trial

- The date of the last assessment and/or contact. A follow-up contact (telephone or visit) will be arranged as appropriate
- (Serious) Adverse events

Final Assessments:

- Every effort should be made to ensure that all procedures and evaluations scheduled for the Early Discontinuation Visit are performed.
- Retrieve all study medications from the subject.

Discontinuation for Virologic Failure

Subjects who discontinue because they have met criteria for virologic failure (Section 4.2.3.1.1.2) while on study therapy should complete an Early Discontinuation Visit as outlined in the Trial Flow Chart (Section 6.0), and return to the study site for follow-up visits at 4, 8, 12, and 24 weeks following confirmation of virologic failure.

Subjects who meet the virologic failure criterion for relapse (HCV RNA \geq LLOQ following the end of all study therapy, after becoming undetectable [TND] at the end of treatment) will return to the study site for the remainder of their follow-up visits (e.g., 4, 8, 12, and 24 weeks) as outlined in the Trial Flow Chart (Section 6.0).

All subjects who take at least 1 dose of study drug, experience virologic failure, and complete FW24 should be offered long-term follow-up (see Section 7.1.5.6).

Discontinuation during Follow-Up Period(s)

Subjects who discontinue during the follow-up period (e.g. follow-up visits at 4 through 24 weeks after EOT) for reasons other than virologic failure should complete an Early Discontinuation Visit as outlined in the Trial Flow Chart. Subjects who discontinue from the long-term follow-up period (e.g. through 3 years after EOT) should complete an Unscheduled Visit as outlined in the Long-Term Follow up section of the Trial Flow Chart.

At a minimum, the following information should be collected:

- The reason the subject discontinued
- The date of the last assessment and/or contact. A follow-up contact (telephone or visit) will be arranged as appropriate
- SAEs (per reporting requirements outlined in Section 7.2)

Discontinuation of Long Term Follow-Up

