The mFAS population will be used for the efficacy endpoints of SVR₁₂ and SVR₂₄ as a supportive analysis and for the endpoint of the proportion of subjects experiencing virologic failure at FW12 as a primary analysis. The mFAS population is a subset of the FAS population, with subjects excluded for study discontinuation for reasons unrelated to the treatment regimen. Examples include loss to follow-up, discontinuation from the study due to non-drug related AEs, informed consent withdrawal, and other non-virologic failures.

The final determination on the exclusion of subjects from various analysis populations will be made prior to the final database lock and will be documented in a separate memo.

Subjects will be included in the treatment arm to which they are allocated for the analysis of efficacy data using the FAS, mFAS, and PP populations. Details on the approach to handling missing data are provided in Section 8.6, Statistical Methods.

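### TRD=F and the mFAS and PP exclusions depend on why a subject left the study, so a subject taken off drug for a drug-related event and later lost, with no virologic failure on record, is excluded from SVR12 and SVR24 instead of counted as a failure

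*Combined protocol and SAP*

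**What the plan says.** Section 8.6.1 sorts non-intermittent missing HCV RNA results into two types. Type 2, scored as failure, is introduced with "For missing values due to premature study discontinuations due to treatment related reasons either for safety or efficacy". Type 3 is treated as missing at random and covers study discontinuation for "reasons unrelated to treatment such as loss to follow-up, protocol deviation, withdrawal of consent, administrative reasons, etc". Under TRD=F, a type 3 subject with no virologic failure on record "will be excluded from the analysis for the time points following their study withdrawal". There is one stated override: subjects with documented virologic failure, "even if they withdrew prematurely due to reasons not related to study drug, are classified as failures".

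The analysis populations use the same key. Section 8.5.1 removes from mFAS those who left the study for reasons unrelated to the regimen: "Examples include loss to follow-up, discontinuation from the study due to non-drug related AEs, informed consent withdrawal, and other non-virologic failures". Table 16 gives non-treatment-related study discontinuation as a ground for exclusion from both PP and mFAS. Table 15 makes PP with TRD=F the primary approach for SVR12 and SVR24. mFAS with TRD=F and FAS with M=F are supportive for those two endpoints, and mFAS with TRD=F is the primary approach for virologic failure at FW12.

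Stopping drug and leaving the trial are separate events in the protocol. In section 5.8, Table 10 has a row for a Grade 4 laboratory, life-threatening or hospitalising event "that is assessed to be a study drug-related laboratory or clinical AE". Its action is to stop treatment while monitoring in the trial continues. Section 7.1.5.4 adds that subjects who stop therapy early "should have an Early Discontinuation visit and then continue into follow-up visits".

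**The concern.** The rule's name, and the type 2 label referring to the study drug, suggest that a course cut short by the drug should count against the regimen when the outcome is unknown. The operative wording does this only if the drug-related event is also the recorded reason for leaving the study. A subject who stops drug for such an event, agrees to follow-up as the protocol encourages, and is then lost has a second, separate reason for leaving. That reason is on the type 3 list without qualification, and nothing carries the first reason forward.

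Two subjects with the same event and the same missing FW12 result can therefore be scored differently, depending only on whether the second first entered follow-up. The missing-at-random premise given for type 3 is also hard to defend for someone whose treatment was shortened by the drug. At stake are the primary PP estimate and the supportive mFAS estimate of SVR, in arms small enough for one subject to show.

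**Working it through.** **Step 1: trace the rule.** Take subjects who permanently stop drug for an event assessed as drug-related.

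- *Leaves the study at once, event as reason:* type 2, failure.
- *Stays and has an FW12 result:* classified on the observed HCV RNA.
- *Never below LLOQ on treatment, with HCV RNA detected when treatment ends:* non-response under 4.2.3.1.1.2, so a failure whatever follows.
- *Confirmed rebound, breakthrough or relapse before leaving:* documented virologic failure, so a failure.
- *Misses FW12 but has results on either side:* handled by the intermittent-missing rule.
- *No failure documented, then lost or withdraws consent before FW12:* type 3, excluded from PP and mFAS.

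Only the last case is affected. For SVR24 the same applies with FW24 in place of FW12.

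**Step 2: inputs.** Section 8.9.1 gives PP sizes of 45 (50 × 0.90) and 22 (25 × 0.90 = 22.5). The documents give no number of affected subjects, k, so k = 1 to 3 is assumed.

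**Step 3: reproduce the plan's figures.** For x successes in n, the Clopper-Pearson 95% limits are the 0.025 quantile of Beta(x, n − x + 1) and the 0.975 quantile of Beta(x + 1, n − x). When x = n the limits are 0.025^(1/n) and 100%. This gives 43/45 = 95.6% (84.9, 99.5) and 20/22 = 90.9% (70.8, 98.9). All eight rows of Table 19 match.

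**Step 4a: planned PP size is what remains after exclusion.** Excluded as written, the estimate is x/n. With the k subjects returned as failures it is x/(n + k).

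| k | Arms 1–4, 43/(45 + k) | Arms 5–6, 20/(22 + k) |
|---|---|---|
| 0 (as written) | 95.6% (84.9, 99.5) | 90.9% (70.8, 98.9) |
| 1 | 93.5% (82.1, 98.6) | 87.0% (66.4, 97.2) |
| 2 | 91.5% (79.6, 97.6) | 83.3% (62.6, 95.3) |
| 3 | 89.6% (77.3, 96.5) | 80.0% (59.3, 93.2) |

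One subject moves the estimate by 95.6 − 93.5 = 2.1 points or 90.9 − 87.0 = 3.9 points. It moves the lower limit by 84.9 − 82.1 = 2.8 or 70.8 − 66.4 = 4.4 points.

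**Step 4b: the k subjects are inside the planned size.** Counted as failures the estimate is x/n; excluded it is x/(n − k).

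- 43/45 = 95.6% becomes 43/44 = 97.7% (88.0, 99.9) with k = 1, and 43/43 = 100% (91.8, 100) with k = 2.
- 21/22 = 95.5% (77.2, 99.9) becomes 21/21 = 100% (83.9, 100) with k = 1, a move of 4.5 points.

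The k = 2 case of 45 and the 21/22 case assume that the affected subjects are the arm's only failures.

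**Step 5: how often.** Section 4.1.2.2.2 reports no discontinuations due to AEs among 240 subjects in Part A of PN011 and PN012. The two-sided 95% upper limit is 1 − 0.025^(1/240) = 1.5%. Even at that rate, two or more AE stops of any kind among 45 has probability 1 − 0.985^45 − 45 × 0.015 × 0.985^44 = 1 − 0.507 − 0.347 ≈ 0.15, before requiring later loss with no failure seen. Part A tested 8-week three-drug regimens in treatment-naïve, non-cirrhotic subjects, so this is only indicative.

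**The case against.** The strongest reply is that the gap is narrow and already visible. HCV RNA is scheduled at treatment visits, at Early Discontinuation and at FW4 and FW8, and documented failure overrides the exclusion, so many true failures among early stoppers are caught. FAS with M=F counts every remaining case as a failure. The trial is for estimation only, PP was chosen deliberately, and exclusions are fixed in a memo before database lock. The name TRD=F shows what was meant.

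Most of this stands as a limit on size. It does not remove the point. FAS is supportive, and it also fails unrelated losses and scores reinfection differently, so its gap from PP does not isolate this effect. The memo leaves the classification to judgement in an open-label trial where section 8.2 allows efficacy analyses during conduct.

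A reader might infer three stronger things that the documents do not support:

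- *That every safety stop in Table 10 is affected.* The rows for ALT/AST above 500 IU/L, ALT/AST with bilirubin or INR, creatinine, and eGFR carry no causality condition. The clear cases come from rows that state drug-relatedness.
- *That the bias is always upward.* Exclusion is always higher than scoring a failure, but that comparison is with the rule's own intent. Against true SVR, excluding a subject who would have been cured lowers the estimate.
- *That earlier studies show such cases are common.* In Part C, 1 of 24 withdrew after one dose with AEs. That was a retreatment regimen with ribavirin, and the text does not say that the AEs were drug-related or that the subject was followed and then lost.

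**Conclusion.** The point holds as a gap in definition. As written, a subject permanently taken off drug for an event assessed as drug-related, kept in follow-up, then lost or withdrawn before FW12 with no documented virologic failure, is excluded from the primary PP and supportive mFAS SVR12 and SVR24. Subjects with an FW12 result, or with documented non-response, rebound, breakthrough or relapse, are scored correctly for SVR12. No stated figure in the plan is wrong.

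Measured against what TRD=F sets out to do, each such exclusion raises SVR by about 2 points in an arm of 45 and about 4 to 4.5 points in an arm of 22. The number of such subjects is an assumption and probably low. The change is worth making because the arms are small, the primary estimate is affected, and the correction is cheap.

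**What to change.** **SVR12 and SVR24.** In 8.6.1, define type 2 as a non-intermittent missing result where either the permanent treatment stop or the study discontinuation was for a treatment-related reason (safety or efficacy), whatever reason is later given for leaving. Limit type 3, the mFAS and PP exclusions in 8.5.1, and the matching cells of Table 16 to subjects for whom neither reason is treatment-related.

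**Virologic failure at FW12.** TRD=F on mFAS is the primary approach here, so the wider type 2 must not carry over unchanged. State that these subjects are not counted as virologic failures without observed viraemia.

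**Cost.** SAP wording and a derivation rule, with the endpoint-specific limit above. No new data are needed, because section 7.1.5.4 already collects a discontinuation reason in both the treatment and the follow-up period. The reported SVR may be slightly lower.

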3.2 Secondary Objective(s) & Hypothesis(es)

Objectives will be evaluated separately for each HCV GT.

- 1) **Objective:** To evaluate the efficacy of co-administered MK-3682 (450mg) + MK-8408 (60mg) following 12 weeks of treatment, as assessed by the proportion of subjects achieving SVR₂₄ (Sustained Virologic Response 24 weeks after the end of all study therapy), defined as HCV RNA < LLOQ 24 weeks after the end of all study therapy.
- 2) **Objective:** To evaluate the efficacy of 12 weeks of treatment with co-administered MK-3682 (450mg) + MK-8408 (60mg), as assessed by the proportion of subjects

who experience virologic failure (either on-treatment failure or relapse post-treatment) at Follow-up Week 12 among subjects who do not discontinue study for non-treatment-related (e.g., administrative) reasons.

- 3) **Objective:** To evaluate the effect of baseline resistance-associated variants (RAVs) in NS5A and/or NS5B on the efficacy of 12 weeks of treatment with co-administered MK-3682 (450mg) + MK-8408 (60mg), as assessed by the proportion of subjects with baseline RAVs achieving SVR₁₂.

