8.4.1 Efficacy /Pharmacokinetics Endpoints

8.4.1.1 Efficacy Endpoints

An initial description of efficacy measures is provided in Section 4.2.3.1.

The primary efficacy endpoint is the proportion of subjects achieving SVR₁₂ after 12 weeks of treatment.

The secondary efficacy endpoints are:

- 1) the proportion of subjects achieving SVR₂₄ after 12 weeks of treatment.
- 2) the proportion of subjects experiencing virologic failure (either on-treatment failure or relapse post-treatment) at Follow-up Week 12 after 12 weeks of treatment, among all subjects who do not discontinue the study for non-treatment-related reasons.

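### The FW12 virologic-failure endpoint is analysed with TRD=F, so a drug-related safety dropout with no FW12 result is counted as a virologic failure

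*Combined protocol and SAP*

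**What the plan says.** Section 3.2 frames secondary objective 2 as the proportion of subjects "who experience virologic failure (either on-treatment failure or relapse post-treatment) at Follow-up Week 12". Section 8.4.1.1 repeats this for the endpoint: "the proportion of subjects experiencing virologic failure (either on-treatment failure or relapse post-treatment) at Follow-up Week 12 after 12 weeks of treatment". Section 4.2.3.1.1.2 lists four categories of virologic failure (non-response, rebound, breakthrough, relapse). Each is defined by HCV RNA; leaving the study is not one of them.

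Section 8.6.1 then sets the analysis. On population and method: "95% CIs for these rates will be calculated based on the mFAS analysis population using the Clopper-Pearson method". On missing data: "The missing data approach of TRD=F described previously will be utilized for this analysis". The last row of Table 15 agrees.

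TRD=F works as follows: "Subjects with treatment-related missing data (type #2 above) will be considered as failure". Type 2 missingness is missing data after "premature study discontinuations due to treatment related reasons either for safety or efficacy, the missing values will be considered as treatment failures".

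Section 8.5.1 fixes the denominator: "The mFAS population is a subset of the FAS population, with subjects excluded for study discontinuation for reasons unrelated to the treatment regimen". The only adverse-event dropouts it names for removal are those with "discontinuation from the study due to non-drug related AEs".

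Section 8.6.1 also says that Table 16 supplies the criteria for the SVR endpoints and for this one. The mFAS row of Table 16 has a single response/non-response pair, split at the LLOQ for the baseline infection.

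**The concern.** The definition and the analysis rule do not match. Under the definition, an event is something seen in HCV RNA. Under the rule, it is also a missing value that follows a drug-related safety withdrawal. TRD=F is a sensible convention for SVR12, where a drug-related dropout without an outcome is reasonably a treatment failure. Carried over to an endpoint called virologic failure, it relabels a tolerability outcome as an antiviral one.

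Two things are at stake. The rate can be too high as a measure of virologic failure, in arms small enough for one subject to be visible. And this endpoint, listed as key secondary in Section 8.1, adds essentially nothing to the supportive mFAS SVR12 analysis, which uses the same population, time point, missing-data rule and reinfection rule.

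**Working it through.** **Tracing one subject.** Take a subject who stops for a drug-related adverse event with HCV RNA undetectable, leaves the study, and has no FW12 sample.

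- Denominator (8.5.1): the reason is related to treatment, so the subject stays in the mFAS.
- Missing-data type (8.6.1): treatment-related and non-intermittent, so type 2.
- TRD=F (8.6.1, Table 15): counted as a failure, so in the numerator.
- Section 4.2.3.1.1.2: no category is met.

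No other text exempts this subject.

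**Interval method.** The plan gives no figure for this endpoint, so I checked the method on Table 19. Clopper-Pearson limits from beta quantiles reproduce all eight rows, for example 43/45 = 95.6% (84.9, 99.5) and 20/22 = 90.9% (70.8, 98.9).

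**Inputs.** Let n be the mFAS size of an arm, v the subjects with an observed virologic failure, and s the drug-related safety dropouts without one and with FW12 missing. The plan states neither n nor s.

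- For n, I use the per-protocol sizes in Section 8.9.1 (45 and 22) and the enrolment targets (50 and 25) as a range.
- For s, I show 1 or 2 as illustrations.

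**Formulas.** Reported virologic failure = (v + s)/n. Rate by definition, with dropouts kept in the denominator = v/n. Excess = s/n.

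Excess per dropout: 1/50 = 2.0 to 1/45 = 2.2 points in Arms 1-4; 1/25 = 4.0 to 1/22 = 4.5 points in Arms 5-6.

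| n | v | s | Reported under TRD=F | By definition |
|---|---|---|---|---|
| 45 | 2 | 1 | 3/45 = 6.7% (1.4, 18.3) | 2/45 = 4.4% (0.5, 15.1) |
| 50 | 2 | 1 | 3/50 = 6.0% (1.3, 16.5) | 2/50 = 4.0% (0.5, 13.7) |
| 22 | 0 | 2 | 2/22 = 9.1% (1.1, 29.2) | 0/22 = 0% (0, 15.4) |
| 25 | 0 | 2 | 2/25 = 8.0% (1.0, 26.0) | 0/25 = 0% (0, 13.7) |

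With s = 0 the two columns agree.

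**Relation to mFAS SVR12.** Under the Table 16 pair, SVR12 = (n − v − s)/n, so the two rates sum to 100%. For n = 45, v = 2, s = 1, SVR12 is 42/45 = 93.3% (81.7, 98.6). Its limits mirror those for failure: 100 − 98.6 = 1.4 and 100 − 81.7 = 18.3.

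Under Section 4.2.3.1.1.2 the identity is close but not exact. Let a be the subjects counted in neither rate and b those counted in both. The sum is then 100% + 100(b − a)/n.

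- Neither: HCV RNA at or above LLOQ at FW12 that is not confirmed, since relapse needs confirmation.
- Neither: TD(u) at end of treatment and quantifiable afterwards, since relapse needs TND at end of treatment.
- Both: confirmed on-treatment breakthrough or rebound with HCV RNA below LLOQ at FW12.

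**The case against.** **The effect may be nil.** Only leaving the study with FW12 missing triggers the rule. Table 10 and Sections 7.1.4.1 and 7.1.5.4 direct most subjects who stop treatment into continued follow-up, so FW12 RNA will usually be observed. No subject discontinued for an adverse event among 240 in Part A of the earlier three-drug studies. This stands, and it limits the size. It does not make the case impossible: in Part C of those studies, one of 24 subjects withdrew after a single dose with vomiting and tachycardia (the regimen included ribavirin, and relatedness is not stated).

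**Virologic events are already reported separately.** Section 8.6.1 promises rates of non-response, rebound, breakthrough and relapse, and Table 17 gives discontinuation due to AE with intervals. The first is descriptive, with no stated population, interval or missing-data rule. It helps a reader but does not repair the formal endpoint.

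**The rule is conservative.** Counting dropouts as failures cannot flatter the regimen. True, but the endpoint is an estimate of virologic failure, and a bias in a known direction is still a bias.

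**The mFAS text may already exclude these subjects.** Its examples of exclusions end with a catch-all for other failures that are not virologic. The governing condition is a reason unrelated to the regimen, and only non-drug-related adverse events are named, so I read drug-related dropouts as kept. The wording is loose enough to need clarifying.

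**Stronger readings.** A reader might infer that the endpoint is always exactly one minus mFAS SVR12, or that SVR12, virologic failure and non-virologic failure must sum to 100%. Neither holds under Section 4.2.3.1.1.2, because of the edge cases above. A reader might also infer that the plan says the endpoint exists to isolate antiviral failure. It does not; that follows only from how the endpoint is defined.

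**Conclusion.** The plan is wrong as written on this row: following it can report virologic failures in subjects who had none. The overstatement is 2.0-2.2 points per drug-related safety dropout in Arms 1-4 and 4.0-4.5 points in Arms 5-6, if the mFAS lies between the per-protocol size and the enrolment target. The number of such dropouts is not given and is probably small; at zero, the estimate does not change. Even then, under the Table 16 criteria, the endpoint only restates mFAS SVR12.

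The documents do not support a claim that the trial's main result is compromised. The endpoint is secondary and estimation-only. The primary per-protocol SVR12 analysis, the sample size and the interim rule are unaffected.

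**What to change.** For this endpoint only:

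1. Count as events subjects with an observed virologic failure of the baseline infection under Section 4.2.3.1.1.2.
2. Keep treatment-related safety discontinuations without virologic failure in the mFAS denominator, and report them on a separate line as non-virologic failure.
3. Replace TRD=F in the last row of Table 15 with this rule, and give the endpoint its own criteria in Table 16.
4. Assign each edge case to a named category: unconfirmed HCV RNA at or above LLOQ at FW12; TD(u) at end of treatment then quantifiable; on-treatment breakthrough or rebound with RNA below LLOQ at FW12; efficacy-related discontinuation with missing data. Do not state that the lines sum to 100% unless this is done.
5. Clarify the closing catch-all in the mFAS exclusion examples in Section 8.5.1.

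The cost is SAP wording, a Table 16 row and one added output line, with no new data. Section 8.0 already provides the supplemental SAP as the route for changes before database lock.
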